MMC 2015-63 Belladonna and Opium rectal suppository effect on postoperative pain and nausea following Total Laparoscopic and Robot-Assisted Hysterectomy.

01/18/2017

B&O for TLH Post-operative Pain and Nausea Study Protocol

This study is a single-center, double-blind, randomized placebo-controlled trial to assess the impact of immediate postoperative Belladonna and Opium rectal suppository use on postoperative pain and nausea following total laparoscopic and robot-assisted hysterectomy. Study activities to take place at Mercy Medical Center, involving both outpatient and inpatient surgical settings. The duration of the trial will be 12 months, with a goal of enrolling 130 patients during this time period. Patients eligible for trial participation are women between ages 18 and 75 undergoing level I total laparoscopic or robot-assisted hysterectomy with or without bilateral salpingo-oophorectomy, with or without cystoscopy performed post-procedure, with or without lysis of adhesions, and with or without surgical treatment of endometriosis, with no additional surgical procedures being performed (i.e. no lymph node dissection or urogynecologic suspension or sling procedures). Patients will be excluded from the study if they have contraindications to the use of B&O suppositories: these contraindications are glaucoma, severe hepatic or renal disease, bronchial asthma, history of narcotic idiosyncracies, respiratory depression, convulsive disorders, acute alcoholism or delirium tremens, or regular use of an anticholinergic medication (twice per week or more frequently). Patients will be withdrawn from the study if the original planned surgery is not performed. If the original planned study is not performed, a suppository will not be placed following surgery. Patients may also opt to withdraw from the study, or may be withdrawn from the study if there is a failure of the research team to adhere to the study protocol. There will be no financial incentives offered for trial participation.

Only the patients of clinical investigators from this trial will be considered for participation in this study. Clinical investigators posting patients for total laparoscopic or robotic hysterectomy at Mercy Medical Center will inform patients of the presence of the clinical trial at the time of surgical posting, using an IRB-approved script (appendix A). The chart number of patients posted for total laparoscopic or robot-assisted hysterectomy will be forwarded to the co-investigator by the clinic surgical coordinator at the time of surgical posting. The co-investigator will review each chart and conduct a telephone interview with each patient prior to surgery to verify trial eligibility and to answer any questions about the trial. Patients will be made aware that study participation is voluntary, and that if they chose to not participate, they will receive standard postoperative pain and nausea pharmacologic management. On the day of surgery, a member of the research team will meet with the patient pre-operatively in a private pre-operative holding area to review and sign a written consent for participation in the trial (Appendix B). This member of the research team would be familiar with the study protocol and risks of the pharmacologic intervention under investigation. These steps will allow patients to be fully informed, and will ensure patient safety and support during the short interval of the study.

On the day of surgery, patients will be randomized to either B&O rectal suppository or to a placebo of glycerin rectal suppository. This study employs a glycerin rectal suppository as a placebo because this over-the-counter medication has limited effects, similar to those of a Belladonna & Opium Suppette, and is similar in size, physical appearance and mechanical properties to a Belladonna & Opium Suppette. A placebo-free comparison group will not be used, as this would change the study design from a double-blind clinical trial to a single-blind clinical trial, with greater potential for investigator bias to influence study results. Additionally,

it is not thought that results for a placebo-free comparison group would substantially differ from those of a glycerin suppository placebo group, and would require a larger study population and greater study resources to achieve findings of similar significance and power. Randomization is to be performed by a biostatistician, with a sealed envelope to be created for each patient containing information regarding randomization to either placebo or intervention group. In the operating room, this envelope will be opened, and the circulating nurse would draw the indicated medication from the Pyxis system. Drug dictionary entries will be created within the Pyxis system by the Mercy Medical Center Department of Pharmacy, so that the Belladonna & Opium Suppette #16A (16.2mg / 60mg), and the glycerin suppository are represented as “Protocol Drug #1” and “Protocol Drug #2”. The patient’s electronic medical record will reflect that “Protocol Drug #1” or “Protocol Drug #2” was received by the patient, so that the nurses caring for the patient postoperatively will be blinded as to which suppository the patient received.

A suppository will be placed rectally by a member of the surgical team at the conclusion of surgery, prior to departure from the OR and awakening from anesthesia. Post-operative placement was selected to minimize interaction with intraoperative anesthetic and analgesic medications, to maximize peak plasma concentrations and therapeutic efficacy of Belladonna alkaloids and Opium within the immediate postoperative period, and control for variation in procedure length between study participants. The nurses caring for the patient postoperatively will be blinded to which suppository the patient did receive, but will be made aware that the patient had received a suppository containing either glycerin or one containing belladonna 16.2mg and opium 60mg, equivalent to approximately 6mg of morphine. These nurses will be educated about potential side effects of Belladonna & Opium suppositories, and of potential drug interactions; they will be asked to document and to inform the covering provider of the occurrence of any such adverse effects. Patients remaining in the hospital overnight following their surgery will undergo a postoperative exam by a resident physician familiar with the study protocol and familiar with potential side effects of the B&O suppository; this physician will inquire about and document the presence of any such side effects. Standard of care at Mercy Medical Center is for nurses to assess patient’s postoperative pain by visual analog scale at regular time intervals. Data regarding patients’ visual analog pain scores for the first 12 hours following surgery will be extracted from the electronic medical record and analyzed by the research team. PO and IV narcotic use in IV morphine equivalents, PO and IV NSAIDs, and PO and IV antiemetic use will also be assessed over the first 12 following surgery, this data is to be extracted from the electronic medical record and analyzed by the research team. Study surveillance will not extend beyond the duration of the participant's postoperative hospitalization, usually less than 24 hours.

The costs of the Belladonna & Opium Suppettes and glycerin rectal suppositories used in this study will be covered by University of Maryland Medical Center, Department of Obstetrics, Gynecology and Reproductive Sciences as a supported resident research project. The costs of glycerin suppositories will be covered by Mercy Medical Center Pharmacy.

We do not anticipate that study participation will result in any uncovered medical costs, as serious side effects from Belladonna and Opium suppositories are estimated at less than 1% occurrence; however, if such adverse medical reactions were to occur, it would be within the postoperative setting and any associated medical costs would be billed to the patient's insurance company as part of the bundled cost of postoperative care.

Due to their historical use, B&O rectal suppositories have not undergone the rigorous Phase I and II clinical trials required of modern pharmaceuticals seeking FDA approval [1], but are available while the FDA makes determinations of efficacy – a regulatory category shared by drugs hydrocodone and morphine [2,3,4]. Common side effects of B&O suppository are related to anticholinergic activity and include dry nose, mouth, throat, skin, and constipation. Serious side effects are estimated at less than 1% occurrence and include orthostatic hypotension, ventricular fibrillation, tachycardia, palpitation, confusion, drowsiness, headache, loss of memory, fatigue, ataxia, CNS depression, rash, antidiuretic hormone release, bloated feeling, nausea, vomiting, biliary tract spasm, dysuria, urinary retention, urinary tract spasm, increased intraocular pain, blurred vision, weakness, respiratory depression, histamine release, physical and psychological dependence, and diaphoresis [5]. Patients enrolled in this trial would be monitored for development of side effects with review to be performed by investigators on a rolling basis.

Scopolamine is an alkaloid with antiemetic properties that is contained within extract of Belladonna. A scopolamine transdermal patch contains 0.6mg of scopolamine alkaloid, and is sometimes used in the pre-operative setting to reduce nausea and emesis in patients reporting a history of motion sickness or of postoperative nausea and vomiting. The recommended dose of scopolamine for use pre-operatively is 0.3 to 0.65mg [6]. Based on the USP Pharmacopeia and gas chromatography data on belladonna extract [7,8], the B&O rectal suppository contains less than 0.02mg of scopolamine, making the total dose of scopolamine received by a patient with a scopolamine patch and a B&O suppository 0.62mg, which is less than the recommended upper limit of dosing for the operative setting. For this reason, patients receiving a pre-operative scopolamine patch will not be excluded from participation in this trial.

The primary hypothesis of the study is that the use of a B&O rectal suppository is associated with decreased postoperative pain and nausea following total laparoscopic or robot-assisted hysterectomy. The visual analog scale (VAS) to be used for assessment of postoperative pain has been demonstrated to be linear in the setting of mild-to-moderate pain [9], such that a 15% decrease in VAS score corresponds to a 15% decrease in subjectively experienced pain. Minimal clinically significant difference in score on the VAS has been shown to occur at approximately 11-14 mm regardless of pain severity [10]. Sample size calculation is based on VAS pain scores following laparoscopic hysterectomy as reported by Ghezzi, et al. [11]. Sample size is set at 65 patients per group (total trial enrollment of 130 patients) with a goal of detecting a 30% decrease in mean VAS score with 80% power, using $p = 0.05$ as a criteria for statistical significance, and accounting for a rate of up to 15% for trial withdrawal, incomplete data, and loss-to-follow-up [12].

For statistical methodology, patient characteristics for the two study arms will be analyzed using a two-sided Student's t-test for continuous variables, or a χ^2 test for categorical variables and proportions. To assess for clinical superiority of the B&O suppository intervention, one-sided Student's t-test (for continuous outcomes) or a one-sided Fisher's Exact test (for categorical outcomes) will be used. One-sided tests are to be used since the addition of B&O is not expected to increase pain, narcotic use, recovery time, or need for rescue anti-emetics a priori. Fisher's Exact test was chosen as a more conservative measure for assessing outcomes, and due to the availability of a one-sided test. A linear regression will be performed on the outcome of PACU discharge readiness time using several different model specifications in order to check for robustness of results.

Bibliography

- [1] CEO of Amerifit Brands, Inc., Nov 7, 2007 Gail T. Costello to Cyrill Siewert.
<http://www.fda.gov/ICECI/EnforcementActions/WarningLetters/2007/ucm076570.htm>.
- [2] Alexander, Thomas J. Lauterio, and Matthew W. Davis Nasr, "Unapproved drugs in the United States and the Food and Drug Administration," *Advances in therapy*, vol. 28, no. 10, pp. 842-856, October 2011.

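### Regular opioid users are eligible, but preoperative opioid use is neither stratified on nor adjusted for in the comparisons of pain and narcotic use

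*Combined protocol and SAP*

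**What the plan says.** The opening paragraph of the study protocol introduces its exclusions this way: "Patients will be excluded from the study if they have contraindications to the use of B&O suppositories". Among them is "regular use of an anticholinergic medication (twice per week or more frequently"). The items closest to opioids are in the run "history of narcotic idiosyncracies, respiratory depression, convulsive disorders, acute alcoholism or delirium tremens". These concern abnormal reactions to narcotics and a respiratory state. A woman who takes an opioid regularly and has neither is eligible.

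The recruitment paragraph sets up the check on eligibility: "The co-investigator will review each chart and conduct a telephone interview with each patient prior to surgery to verify trial eligibility". Randomization follows on the day of surgery, from sealed envelopes prepared by a biostatistician. No stratification factor is named.

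The paragraph on suppository placement and data collection describes the active product as "belladonna 16.2mg and opium 60mg, equivalent to approximately 6mg of morphine". It then sets the outcomes. For pain: "Data regarding patients’ visual analog pain scores for the first 12 hours following surgery will be extracted from the electronic medical record". For drug use over the same window: "PO and IV narcotic use in IV morphine equivalents, PO and IV NSAIDs, and PO and IV antiemetic use will also be assessed".

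The statistical methodology paragraph compares continuous outcomes by a one-sided Student's t-test. Its only regression is for PACU discharge readiness time, with covariates unnamed. Patient characteristics are to be compared between arms but are not listed.

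**The concern.** Preoperative opioid use plausibly predicts both postoperative pain and postoperative opioid consumption. A regular user's maintenance dose, if given in hospital, would enter the 12-hour narcotic total alongside doses given for surgical pain, since the plan does not separate the two. If tolerance blunts the response to the opium component, the average treatment effect is diluted as well.

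Nothing later in the plan deals with this. The outcome tests carry no covariate, and prior opioid use is not named as a variable to be collected. If it is not recorded before randomization, it cannot be adjusted for cleanly afterwards. At stake is precision in a small trial, on the secondary narcotic outcome and to a lesser degree on VAS, the outcome on which the trial is sized.

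**Working it through.** **The plan's own figure.** "Sample size is set at 65 patients per group (total trial enrollment of 130 patients"), allowing for up to 15% loss. Evaluable per arm: 65 × 0.85 = 55.25, about 55. The documents give no mean or SD for VAS, so the 65 cannot be reproduced directly. Working backwards, a coefficient of variation of about 0.63 (one-sided) or 0.56 (two-sided) gives 55 evaluable and 65 enrolled per arm. This point does not depend on that figure.

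**Narcotic use: variance with regular users mixed in.** All inputs are assumed, because the documents give none: opioid-naive mean μ = 10 mg and SD s = 7 mg; regular users have mean mμ and SD ms, with m = 2 or 2.5; prevalence p = 5% or 8%.

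- Within-group variance W = (1 − p)s² + p(ms)²
- Between-group variance B = p(1 − p)((m − 1)μ)²
- Total T = W + B. The increase is T/s² with s² = 49. A yes/no covariate removes B, a share B/T.

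| p | m | W | B | T | T/49 | B/T |
|---|---|---|---|---|---|---|
| 5% | 2 | 46.55 + 9.80 = 56.35 | 4.75 | 61.10 | 1.25 | 7.8% |
| 8% | 2 | 45.08 + 15.68 = 60.76 | 7.36 | 68.12 | 1.39 | 10.8% |
| 5% | 2.5 | 46.55 + 15.31 = 61.86 | 10.69 | 72.55 | 1.48 | 14.7% |
| 8% | 2.5 | 45.08 + 24.50 = 69.58 | 16.56 | 86.14 | 1.76 | 19.2% |

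So variance rises by 25% to 76%, and the covariate removes 8% to 19% of the total. It does not remove the wider spread among users themselves: the variance left is 56.35/49 = 1.15 to 69.58/49 = 1.42 times the naive value.

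The result depends on p. At p = 1%, T = 48.51 + 1.96 + 0.99 = 51.46 for m = 2 and 48.51 + 3.06 + 2.23 = 53.80 for m = 2.5, so the increase is only 5% to 10%. At p = 0 it is nil.

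**VAS: dilution of the effect.** Inputs are again assumed: regular users get between none and half of the drug effect, and their pain is 0 to 1 SD higher. With 55 per arm, the standardized effect giving 80% one-sided power is (1.645 + 0.842) × √(2/55) = 0.474. For a share q of users with relative effect e, the mean effect becomes 0.474 × [(1 − q) + qe], and the SD is widened by the mixture.

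Example: q = 5%, e = 0, shift 1 SD.

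- Effect: 0.474 × 0.95 = 0.450
- Arm variances: 1 + 0.0475 × 1² = 1.048 (placebo) and 1 + 0.0475 × 1.474² = 1.103 (active); pooled SD about 1.037
- z = (0.450/1.037) × √(55/2) − 1.645 = 0.63; power about 74%

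Over the full range of e and shift, one-sided power falls from 80% to 74–78% at q = 5%, 67–76% at 10% and 55–72% at 20%.

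**Chance imbalance.** Two extra users at 10 mg above naive move an arm mean by 2 × 10/55 = 0.36 mg; three at 15 mg above move it by 3 × 15/55 = 0.82 mg. The standard error of the arm difference runs from √(2 × 61.10/55) = 1.49 mg to √(2 × 86.14/55) = 1.77 mg. The shift is roughly a quarter to a half of one standard error, and T already includes it.

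**The case against.** The strongest reply is that the list is a contraindication list. Regular anticholinergic use is on it for that reason, not to control outcome variance, and opioids already have items of the same safety kind. A reader might infer that the protocol is inconsistent in screening for one component of the drug and not the other. The stated purpose of the list does not support that. It explains the asymmetry, but the analysis still lacks any handling of prior opioid use.

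Three further inferences are tempting and should be resisted.

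- *That the comparison is biased, or that a few extra users in one arm would decide it.* Randomization balances prior use in expectation. The imbalance worked out above is ordinary sampling noise, and counting it beside the variance increase would count it twice.
- *That the trial loses a known fraction of its information.* The variance ratios correspond to 1 − 1/1.25 = 20% up to 1 − 1/1.76 = 43% of effective sample for narcotic use. Every input is assumed, so this is not an estimate for this trial.
- *That 6 mg is negligible to a regular user.* The documents give no consumption figure. In the illustration users average 20 to 25 mg, so 6 mg is 24% to 30% of that.

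It is also fair to say that the interview questions are not shown and the patient characteristics are not listed. Prior opioid use may therefore be recorded in practice. What can be verified is that neither the criteria nor the analysis mentions it. Finally, taking all eligible hysterectomy patients is a legitimate choice, and excluding regular users would narrow whom the result applies to.

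**Conclusion.** The gap holds as a missed, inexpensive gain in precision. It is not a source of bias, and the documents do not support saying that regular opioid users must be excluded: a twice-weekly threshold is stated for anticholinergics only, with no basis given for opioids.

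The larger quantified cost falls on narcotic use, for which the trial was not sized; the cost for VAS is modest unless regular users are common. Both illustrations rest wholly on assumed prevalence, consumption and response. Adjustment recovers only part of the loss: it removes the difference in level between users and non-users, not the extra spread among users and not any dilution of the effect. That is still better than an unadjusted test at almost no cost.

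**What to change.** Add one item, regular preoperative opioid use (yes/no), to the planned chart review and telephone interview. Define it in advance and record it before randomization. For narcotic use and VAS, replace the unadjusted t-test with a linear model on treatment arm plus this indicator, and report the unadjusted comparison as a sensitivity analysis. List the indicator among the patient characteristics compared by arm, so that readers can see how common regular use was.

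The cost is one interview question and a slightly more complex analysis; eligibility and care do not change. Whether to exclude regular opioid users, and at what threshold, is for the clinical team to decide.

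### Open-ended withdrawal for team protocol failures, with no as-randomized analysis, lets randomized and treated patients drop out of the comparison

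*Combined protocol and SAP*

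**What the plan says.** The opening paragraph of the protocol gives two team-side routes out of the trial. One is mandatory: "Patients will be withdrawn from the study if the original planned surgery is not performed"; in that case no suppository is given. The other is discretionary: patients "may be withdrawn from the study if there is a failure of the research team to adhere to the study protocol". The discretionary rule has no time point, no list of failures that count, no named decision-maker and no blinding condition.

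The timeline comes from the paragraphs on randomization and on suppository placement:

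- Allocation: "On the day of surgery, patients will be randomized to either B&O rectal suppository or to a placebo of glycerin rectal suppository".
- Envelope: it is described as "containing information regarding randomization to either placebo or intervention group", and "In the operating room, this envelope will be opened, and the circulating nurse would draw the indicated medication from the Pyxis system". The text does not say whether this happens before or after the operation is finished.
- Treatment: "A suppository will be placed rectally by a member of the surgical team at the conclusion of surgery".
- Outcomes: "visual analog pain scores for the first 12 hours following surgery will be extracted from the electronic medical record"; narcotic, NSAID and antiemetic use come from the same record.

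The sample-size paragraph sets 65 per group, "accounting for a rate of up to 15% for trial withdrawal, incomplete data, and loss-to-follow-up". The statistical methodology paragraph names the tests. Neither paragraph defines an analysis population, a rule for withdrawn patients' data or a missing-data method.

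**The concern.** Randomization protects the comparison only while patients are counted in the arm to which they were assigned. Here the team may remove a patient because of its own lapse, at any time, including after dosing and after pain scores are in the record. Because withdrawal is budgeted alongside incomplete data and loss to follow-up, the natural reading is that a withdrawn patient leaves the analysis, although no sentence says so.

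If such removals were related to pain or nausea in one arm more than the other, the VAS, narcotic and antiemetic comparisons would all be affected. The outcome tests are one-sided in favour of B&O, so a bias toward B&O would turn directly into false-positive findings; a bias the other way would hide a real effect.

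The rule for operations not performed as planned is a smaller version of the same problem. It acts before treatment, and is harmless if applied before allocation is known, but the plan does not tie the opening of the envelope to completion of the procedure.

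**Working it through.** **Inputs.** From the sample-size paragraph: 65 per group, 30% decrease in mean VAS, 80% power, p = 0.05, up to 15% loss. From the methodology paragraph: one-sided outcome tests. The control mean and SD are not given, and the sidedness of the sample-size calculation is not stated, so both versions are shown.

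**1. The plan's own figure.** 65 × 0.85 = 55.25, so about 55 evaluable per arm; 65 − 55 = 10 may be lost. The standardized effect detectable with 55 per arm is d = √(2/55) × (z_α + z_0.80):

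- one-sided: 0.1907 × (1.645 + 0.842) = 0.474, implying SD/mean = 0.30/0.474 = 0.63
- two-sided: 0.1907 × (1.960 + 0.842) = 0.534, implying SD/mean = 0.30/0.534 = 0.56

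Either ratio gives n = 55 and 55/0.85 = 64.7, rounded up to 65. Without the mean and SD, the figure can be neither confirmed nor faulted.

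**2. Withdrawal unrelated to outcome.** Power = Φ(d√(n/2) − z_α). With n = 55 it is 80% by construction. With n = 65, √(65/2) = 5.701:

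- one-sided: Φ(0.4742 × 5.701 − 1.645) = Φ(1.058) = 85.5%
- two-sided: Φ(0.5342 × 5.701 − 1.960) = Φ(1.085) = 86.1%

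There is no bias in this case. The cost is about 6 percentage points of power if the whole allowance is used.

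**3. Withdrawal related to outcome.** This was simulated under no true effect: 65 per arm, normal outcome, one-sided t-test at 0.05, 40,000 runs per scenario. The patients removed are those highest on a score correlated with pain. The counts and correlations are assumptions, not document figures.

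| Removed | Correlation with pain | Bias in difference (SD) | One-sided type I error |
|---|---|---|---|
| 3 of 65, B&O arm only | 0.3–0.5 | −0.03 to −0.05 | 0.07–0.09 |
| 10 of 65, B&O arm only | 0.3–0.5 | −0.08 to −0.14 | 0.12–0.19 |
| 10 of 65, B&O arm only | 1.0 | −0.28 | 0.50 |
| 10 of 65, each arm | 0.3–0.5 | 0.00 | 0.05–0.06 |
| 10 of 65, each arm | 1.0 | 0.00 | 0.08 |

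**4. Extreme bound.** Removing the top fraction p of a normal distribution moves its mean by −φ(z)/(1 − p), where z cuts off the top p. For p = 0.05: 0.1031/0.95 = 0.11 SD. For p = 0.10: 0.1755/0.90 = 0.19 SD. For p = 0.15: 0.2332/0.85 = 0.27 SD. The last is 0.27/0.534 = 51% to 0.27/0.474 = 57% of the implied design effect. The case of 3 of 65 is 0.03/0.534 = 6% to 0.05/0.474 = 11% of it.

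**The case against.** A reader might infer that the rule does remove patients selectively and so breaks the randomized comparison. The documents do not support that. They permit withdrawal; they do not say that it will depend on outcome, nor state in terms that a withdrawn patient leaves the analysis.

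The obvious stories of how a team failure could follow from pain also fit the timeline poorly:

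- A wrong suppository would be drawn and placed before the patient wakes, so postoperative pain cannot cause that error.
- A missed pain score arises in routine nursing care, so it is not clearly a research-team failure. It is also missing data, which analysis by assigned arm does not restore.
- Off-protocol rescue has no rule to break: the Study Participation Alert Form asks for routine postoperative care, and narcotic and antiemetic use are outcomes.

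Most identifiable team duties (eligibility, consent, allocation, drawing and placing the drug) come before any outcome.

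Nor is it shown that whoever decides on withdrawal knows the arm. The dispensing system and the record show only coded drug names, the two products are described as similar in appearance, and postoperative nurses are blinded. Whether the envelope carries the arm name or the code is not stated.

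Finally, 0.27 SD needs the entire allowance to be team withdrawals, all in one arm and chosen purely as the highest pain scores, whereas the plan spreads the 15% over three causes.

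All of this stands, and it limits the size of the problem. It does not remove it. A failure that occurs before any outcome can still lead to a withdrawal decision taken after the outcomes are recorded, and nothing in the plan requires that decision to be blind or keeps the patient in her assigned arm.

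**Conclusion.** The point holds as a permission left open, not as a demonstrated bias. Followed as written, the plan can drop randomized and treated patients because of the team's own deviations. Withdrawal unrelated to outcome costs power only, and in the simulation, under no true effect, withdrawal acting alike in both arms left the difference unbiased. Differential withdrawal of a few patients gives a small bias with a noticeable rise in false positives (0.07–0.09 against 0.05 for 3 of 65). The figure of 0.27 SD is an upper limit and should not be quoted as the expected effect.

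These sizes rest on an assumed normal outcome, on assumed counts and correlations, and on a design effect solved back from 55 per arm. That withdrawn patients leave the analysis is inferred from the 15% allowance. Severity: should-fix. The defect touches every efficacy comparison and is hard to repair credibly once outcomes have been seen, but its realistic size is modest.

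**What to change.** - Replace the team-failure withdrawal rule. Every patient whose envelope is opened is analysed in the assigned arm, whatever the team's deviation, and her 12-hour record data are still extracted. The exceptions are invalid consent and a patient's own withdrawal of the use of her data.
- Open the envelope only once the planned, eligible procedure is confirmed complete, just before the suppository is drawn. Changed operations then leave before allocation is known.
- Log deviations blind to outcome.
- Show a per-protocol analysis as a sensitivity analysis only.
- State the source of PACU discharge readiness time, which the plan does not give, so that it too can be collected after a deviation.

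The cost is protocol wording, slight dilution of the effect by patients with deviations, and a short wait to draw the drug at the end of surgery. No larger sample is needed: if all 65 per arm have outcome data, power is about 86% at the implied effect, before any dilution.

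### Patients may be withdrawn for the research team's own protocol failures, with no time limit or blinding condition, and nothing keeps them in the analysis

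*Combined protocol and SAP*

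**What the plan says.** The opening paragraph of the study protocol gives three ways out of the study.

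- Change of surgery, which is mandatory: "Patients will be withdrawn from the study if the original planned surgery is not performed". In that case "a suppository will not be placed following surgery", so this exit comes before dosing.
- The patient's own choice.
- Staff failure, which is permissive: a patient "may be withdrawn from the study if there is a failure of the research team to adhere to the study protocol". No qualifying failures, decision-maker, deadline or blinding condition are given.

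On timing and blinding, the protocol says "On the day of surgery, patients will be randomized to either B&O rectal suppository or to a placebo of glycerin rectal suppository", and later "In the operating room, this envelope will be opened, and the circulating nurse would draw the indicated medication from the Pyxis system". It states that "the nurses caring for the patient postoperatively will be blinded as to which suppository the patient received". It makes no such statement about whoever decides on withdrawals.

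The paragraph on suppository placement and data collection describes nurses' pain scoring as standard care. It says the pain scores for the first 12 hours "will be extracted from the electronic medical record and analyzed by the research team"; narcotic, NSAID and antiemetic use are obtained the same way.

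The sample size paragraph sets 65 per group, "accounting for a rate of up to 15% for trial withdrawal, incomplete data, and loss-to-follow-up". The statistical methodology paragraph names tests only. The document does not define an analysis population, mention intention-to-treat or describe how missing data are handled.

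**The concern.** A staff error is not a reason to lose a randomized patient whose outcomes are recorded in routine care whether or not the error occurred. The change-of-surgery rule is tied to no suppository being given, but the staff-failure rule has no such limit. It therefore reaches patients who have already been dosed and whose pain scores may already be in the chart.

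Randomization protects the comparison only if membership of the analyzed set does not depend on later judgement related to arm and outcome. Here such judgement is allowed and is not required to be blind. At stake is every efficacy comparison in the trial: pain, narcotic use, antiemetic use and recovery time. Even where no bias arises, leaving out patients whose data exist wastes information.

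**Working it through.** **1. The plan's own figure.** Inputs from the sample size paragraph are 65 per group, 80% power, 0.05 significance and losses up to 15%. The control mean and SD are not given, so 65 cannot be rebuilt in full. The attrition step can be checked:

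- 55 / (1 − 0.15) = 64.7, which rounds up to 65.
- 65 × 0.85 = 55.25 evaluable per arm, so 65 − 55.25 = 9.75, or about 10 per arm, can be lost within plan.

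The 15% covers withdrawal, incomplete data and loss to follow-up together. The share due to staff failure is unknown.

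**2. Precision.** Assume the standardized effect d is the one that gives 80% power with 55 per arm, using d = (z_α + z_0.80) × √(2/n) and power = Φ(d√(n/2) − z_α).

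- One-sided 0.05: d = (1.645 + 0.842) × √(2/55) = 0.474. At 65 per arm, power = Φ(0.474 × 5.701 − 1.645) = 85.5%.
- Two-sided 0.05: d = (1.960 + 0.842) × √(2/55) = 0.534. At 65 per arm, power = Φ(0.534 × 5.701 − 1.960) = 86.1%.

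Both sidednesses are shown because the sample size sentence does not state one, while the outcome tests are one-sided. The gain from 80% to about 86% is an upper bound. It needs the whole 15% to come from this clause and all of it to be recovered.

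**3. False positives when removals depend on arm and outcome.** Simulation assumptions: no true effect, normal scores, 65 per arm, one-sided t-test at 0.05, 40,000 trials. Patients are removed from the B&O arm only.

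| Removed from B&O | Rejection rate |
|---|---|
| 1 highest pain score | 7.9% |
| 3 highest | 14.8% |
| 5 highest | 23.7% |
| 3 at random from the upper half | 7.4% |
| 5 at random from the upper half | 9.6% |
| 8 at random from the upper half | 14.3% |

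A variant with 20,000 trials also removed the same number of placebo patients at random. It gave 7.8%, 15.2% and 23.1% for 1, 3 and 5 highest.

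**4. False positives when removals ignore arm.** In the same null setting, removing the 2, 6, 10 or 20 highest scores of all 130, whatever the arm, gives 4.8%, 4.7%, 4.8% and 4.9%. Removing 6, 10 or 16 at random from the pooled upper half gives 4.8% to 4.9%. Removing equal numbers from each arm purely at random gives 4.7% to 5.0%. This is expected: with no true effect, a choice that does not use the arm label leaves the labels exchangeable. Steps 3 and 4 concern false positives only.

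**The case against.** The strongest reply is that the clause speaks of leaving the study and does not mention the analysis. Several stronger readings that a reader might infer are not supported.

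- *The protocol prescribes a per-protocol analysis.* It does not use the term or say that withdrawn patients are dropped. That they leave the analysis is inferred from the attrition wording and the absence of any defined population. That dosed patients are covered is inferred from the missing time limit.
- *The trial was sized without these patients.* The 15% is one combined allowance. An allowance for losses does not state who is analyzed, and the part due to staff failure could be close to zero.
- *The people who analyze outcomes decide the withdrawals.* The clause is passive and names nobody. The document says only that the research team extracts and analyzes the data.
- *Any few non-random removals bias the result towards a positive finding.* Step 4 shows otherwise: removals must also be linked to arm. The trial is described as double-blind, a biostatistician randomizes, and the chart carries only a coded drug name. The clearest route to knowing the arm is presence when the envelope is opened, and nothing says those people decide withdrawals.

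These points limit the concern but do not remove it. Blinding of the withdrawal decision is neither required nor described, and no other text settles who is analyzed.

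**Conclusion.** The concern holds in a limited form. The protocol permits discretionary withdrawal after randomization for staff failure, without a time limit or blinding condition, and does not say that such patients stay in the analysis. Read naturally, this allows avoidable exclusions of patients whose outcomes are on record.

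The size depends on how the rule is used. In the worst case, with 1, 3 or 5 removals chosen on both arm and high pain, the one-sided false-positive rate rises from 5% to about 8%, 15% or 24%. This shows the room the rule leaves and does not forecast conduct. With removals blind to arm, the rate stays near 5% and the cost is lost precision, at most about 6 percentage points of power. The simulations assume normal scores and the power figures use a back-solved effect, because the plan gives no mean or SD. The frequency of staff-failure withdrawals is unknown.

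Severity: should fix. The harm is conditional and the repair is cheap.

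**What to change.** Amend the withdrawal text and add an analysis-population statement.

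- Separate withdrawal from study procedures from exclusion from analysis. A consent or eligibility failure found before dosing may still end participation; how that is handled is outside this point.
- State that a deviation by the research team is logged and is not by itself a reason to exclude a randomized patient from the analysis.
- Define the primary analysis as all randomized patients with available chart outcomes, in the arm on the biostatistician's randomization list, subject to consent. This includes patients who, through a staff error, received the wrong suppository or none.
- The exclusion for planned surgery not performed may remain if it is decided before the envelope is opened.
- Present any per-protocol set only as a sensitivity analysis, fixed by someone blind to arm and outcome.

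The cost is a short amendment. No new data collection is needed because outcomes come from the routine record, and no larger sample is needed provided those outcomes are obtained. The downside is slight dilution of the effect if some patients received the wrong suppository or none.
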